Title: TWILIGHT Study - Ticagrelor With Aspirin or Alone in High-Risk
Patients After Coronary Intervention

PI [name]

NCT Number NCT02270242

Date of protocol: 28-Mar-16

Drug Substance	Ticagrelor and Aspirin
Study Number	ISSBRIL0345
EudraCT No.	2014-005498-35
ClinicalTrials.gov ID	NCT02270242
Version Number	4.0
Date	28-Mar-2016

TWILIGHT Study

Ticagrelor With Aspirin or Alone in High-Risk Patients After Coronary Intervention

Funding Agency:

AstraZeneca

Sponsor-Investigator/Academic Research Center (ARC): The Office of Interventional Cardiovascular Research and Clinical Trials at Icahn School of Medicine at Mount Sinai

PROTOCOL SYNOPSIS

Title of Study	TWILIGHT Study - Ticagrelor With Aspirin or Alone in High-Risk Patients After Coronary Intervention
Primary Investigator:	[name], FACC, FACP, FCCP, FESC, FAHA, FSCAI Professor of Medicine and Director of Interventional Cardiovascular Research and Clinical Trials Icahn School of Medicine at Mount Sinai
Study Centers:	Approximately 100 sites in U.S., Canada, South America, Europe, and China
Study Design	Multicenter, prospective, blinded dual-arm study
Purposes	Aim 1: To determine the impact of ticagrelor alone versus ticagrelor plus aspirin in reducing clinically relevant bleeding among high-risk patients who had PCI with at least one drug-eluting stent. Aim 2: To determine the impact of ticagrelor alone versus ticagrelor plus aspirin in reducing ischemic adverse events at one year among high-risk patients undergoing PCI with at least one drug-eluting stent.
Enrollment and Patient Population	Up to 9000 high-risk patients who have undergone successful PCI with at least one locally approved drug eluting stent discharged on DAPT with aspirin and ticagrelor of at least 3 months intended duration.
Primary Objective	The primary objective of this study is to determine the impact of antiplatelet monotherapy with ticagrelor alone versus DAPT with ticagrelor plus aspirin for 12 months in reducing clinically relevant bleeding among high-risk patients undergoing PCI who have completed a 3-month course of aspirin plus ticagrelor.
Secondary Objectives	The secondary objective of this study is to determine the impact of antiplatelet monotherapy with ticagrelor alone versus DAPT with ticagrelor plus aspirin for 12 months in reducing major ischemic adverse events among high-risk patients undergoing PCI who have completed a 3-month course of aspirin plus ticagrelor.
Eligibility Criteria	High-risk patients who have undergone successful PCI with at least one locally approved drug eluting stent AND discharged on DAPT with aspirin and ticagrelor of at least 3 months intended duration will be eligible for the TWILIGHT study.

Enrollment into the study will require meeting at least one clinical inclusion AND at least one angiographic inclusion AND none of the exclusion criteria.

Clinical Inclusion Criteria (MUST MEET AT LEAST ONE):

- Adult patients ≥ 65 years of age
- Female gender
- Troponin positive acute coronary syndrome
- Established vascular disease defined as previous MI, documented PAD or CAD/PAD revascularization
- Diabetes mellitus treated with medications (oral hypoglycemic, subcutaneous injection of insulin)
- Chronic kidney disease defined as an estimated glomerular filtration rate (eGFR) < 60 ml/min/1.73m² or creatinine clearance (CrCl) < 60 ml/min

Angiographic Inclusion Criteria (MUST MEET AT LEAST ONE):

- Multivessel coronary artery disease
- Target lesion requiring total stent length >30 mm
- Thrombotic target lesion(s)
- Bifurcation lesions with Medina X,1,1 classification requiring at least 2 stents
- Left main ($\geq 50\%$) or proximal LAD ($\geq 70\%$) lesion
- Calcified target lesion(s) requiring atherectomy

Exclusion Criteria:

- Under 18 years of age
- Contraindication to aspirin (listed in appendix D)
- Contraindication to ticagrelor (listed in appendix E)
- Planned surgery within 90 days
- Planned coronary revascularization (surgical or percutaneous) within 90 days
- Need for chronic oral anticoagulation
- Prior stroke
- Dialysis-dependent renal failure
- Active bleeding or extreme-risk for major bleeding (e.g. acute gastrointestinal ulcer or history of chronic gastrointestinal ulceration, gastrointestinal pathology with a raised risk for bleeding, malignancies with a raised risk for bleeding)
- Salvage PCI or STEMI presentation.
- Liver cirrhosis
- Life expectancy < 1 year
- Unable or unwilling to provide informed consent
- Women of child bearing potential (as defined in Section 4.2)

	
 • Fibrinolytic therapy within 24 hours of index PCI • Concomitant therapy with a strong cytochrome P-450 3A inhibitor or inducer • Platelet count < 100,000 mm³ • Requiring ongoing treatment with aspirin ≥ 325 mg daily
Randomization	
The eligibility for randomization for all enrolled subjects will be evaluated at the in-person 3-month study visit. Subjects with any of the following will not be randomized:
 
 • Refusal of randomization by subject or treating physician • Withdrawal of consent • Lost to follow-up • Death • Major bleeding (BARC Types 3b or greater) • Occurrence of an ischemic event after PCI such as myocardial infarction, definite or probable stent thrombosis, ischemic stroke, coronary revascularization with drug-eluting stent • No longer taking DAPT with aspirin and ticagrelor • Non physician-guided cessation of aspirin or ticagrelor of 5 consecutive days or greater. • Women of child bearing potential (as defined in Section 4.2) • Renal failure requiring dialysis • Current indication for oral anticoagulation or high dose aspirin
Statistical Methods	
Analysis for Primary Bleeding Endpoint	
The analysis for the primary bleeding endpoint will be performed on the ITT population. The primary objective is to determine if ticagrelor monotherapy is superior to ticagrelor plus aspirin for the primary bleeding endpoint (BARC Types 2, 3 or 5 bleeding). The null hypothesis for this analysis is that the HR for the experimental group (H_0) = 1. The alternative hypothesis is that the HR for the experimental group (H_A) \neq 1. A test of superiority at the two-sided 0.05 level will be performed using a Cox proportional hazard model that includes treatment group as a covariate. A point estimate and two-sided 95% CI for the relative risk as measured by the hazard ratio will be calculated based on the Cox proportional hazards model. Event rates will be estimated at one year and Kaplan-Meier curves will be plotted for the time from randomization to the first occurrence of confirmed BARC Type 2, 3 or 5 bleeding by treatment group. This analysis will be repeated in the per protocol (PP) cohort to support the primary results.


Analysis for Primary Ischemic Endpoint
	
The analysis for the primary ischemic endpoint will be performed on the PP cohort. The primary objective is to determine if ticagrelor monotherapy is non-inferior to ticagrelor plus aspirin for the primary ischemic endpoint (all-cause death, non-fatal myocardial infarction, or stroke). Event rates will be estimated at one year and Kaplan-Meier curves will be plotted for the time from randomization to the first occurrence of confirmed all-cause death, non-fatal myocardial infarction, or stroke or by treatment group. A test of non-inferiority at the one-sided 0.025 level will be performed. . . . Assuming an event rate of 8.0% in the control group, a sample size of 8200 will yield 80% power to exclude an absolute non-inferiority margin of 1.6%. If the upper limit of the 95% CI for the point estimate of the absolute risk difference between groups is less than or equal to 1.6% then the criteria for non-inferiority will be met. This non-inferiority margin translates to a relative risk of 20% assuming the observed event rate equals 8.0% in the control arm.

Statistical Methods
	
Unless otherwise stated, all hypothesis tests will be performed using two-sided tests at the 5% significance level. Continuous variables will be summarized using descriptive statistics including means and standard deviations if normally distributed or median with interquartile ranges for skewed distributions. Discrete variables will be summarized using absolute and relative frequencies.

Sample Size Parameters
	
A cumulative bleeding rate of 4.5% is anticipated between time of randomization and 1 year. Assuming a 2% loss to follow-up and non-compliance / cross-over rate of 4%, the current trial will require 8200 subjects to detect a relative reduction in bleeding of 28% with ticagrelor monotherapy with 80% power and a Type I error of 0.05. It is anticipated that approximately 8% - 10% of enrolled subjects will not be eligible for randomization and therefore 9000 subjects will be enrolled at the time of PCI.

[figure not shown]

TABLE OF CONTENTS	PAGE
TITLE PAGE	1
PROTOCOL SYNOPSIS	2
TABLE OF CONTENTS	7
PROTOCOL SIGNATURE PAGE	11
LIST OF ABBREVIATIONS	12
1. INTRODUCTION	13
1.1 Research hypothesis.....	14
1.2 Rationale for conducting this study	14
1.3 Benefit/risk and ethical assessment.....	15
2. STUDY OBJECTIVES	15
2.1 Primary objective	15
2.2 Secondary objective	16
2.3 Exploratory objectives	16

CRF	Case Report Form
DAPT	Dual Antiplatelet Therapy
DES	Drug Eluting Stent
DSMB	Data Safety Monitoring Board
EC	Ethics Committee
FDA	Food and Drug Administration (U.S.)
FFR	Fractional Flow Reserve
ICF	Informed Consent Form
IND	Investigational New Drug Application (FDA)
IRB	Institutional Review Board
ISS	Investigator Sponsored Study
ITT	Intention-to-Treat (analysis dataset)
IVUS	Intravascular Ultrasound
IXRS	Interactive Voice/Web Response System
LAD	Left Anterior Descending (Coronary Artery)
MI	Myocardial Infarction
NSAID	Non-Steroidal Anti-Inflammatory Drug
NSTEMI	Non ST Elevation Myocardial Infarction
P2Y ₁₂	The P2Y ₁₂ protein is found mainly but not exclusively on the surface of blood platelets, and is an important regulator in blood clotting.
PAD	Peripheral Artery Disease
PCI	Percutaneous Coronary Intervention
PP	Per Protocol (analysis dataset)
SAE	Serious Adverse Event
STEMI	ST Elevation Myocardial Infarction

The following abbreviations and special terms describe other clinical protocols or academic bodies.

Abbreviation or special term	Explanation
BARC	Bleeding Academic Research Consortium
EXCELLENT	Trial Name: Efficacy of Xience/Promus versus Cypher in Reducing Late Loss after Stenting
GUSTO	Trial Name: Global Utilization of Streptokinase and TPA for Occluded Arteries
OPTIMIZE	Trial Name: Optimized Duration of Clopidogrel Therapy following Treatment with the Endeavor Zotarolimus-Eluting Stent in the Real World Clinical Practice
PLATO	Trial Name: Platelet Inhibition and Patient Outcomes Trial
PRODIGY	Trial Name: Synergy between Stent and Drugs to Avoid Ischemic Recurrences after Percutaneous Coronary Intervention
SYNTAX	Trial Name: TAXUS Drug-Eluting Stent versus Coronary Artery Bypass Surgery for the Treatment of Narrowed Arteries
TIMI	Trial Name: Thrombolysis in Myocardial Infarction

1. INTRODUCTION

Pharmacologic platelet inhibition with aspirin and a P2Y₁₂ inhibitor is a requirement in all patients undergoing percutaneous coronary intervention (PCI) with stenting. Such dual antiplatelet therapy (DAPT) is recommended by international guidelines, with duration varying according to clinical presentation (i.e. acute coronary syndrome) or type of stent implanted during PCI (bare metal vs. drug eluting)(1-3). The paradigm for DAPT is shifting to shorter durations, as evidenced by most recent ESC /EACTS Guidelines on myocardial revascularization giving a class Ib recommendation for 6 months of DAPT after DES (4). While clopidogrel is the most widely used P2Y₁₂ inhibitor, its efficacy is hampered by substantial variability in platelet inhibition that may be attributable to clinical, genetic and procedural parameters (5-8). Moreover, although the novel thienopyridine prasugrel has a more potent and consistent effect on platelet inhibition (9, 10), bleeding risk is significantly higher compared to clopidogrel in acute coronary syndrome (ACS) patients following PCI (11). In contrast, ticagrelor, an oral, reversible, direct-acting inhibitor of the adenosine diphosphate P2Y₁₂ receptor (12) has proven faster, greater and more consistent P2Y₁₂ inhibition than either clopidogrel or prasugrel (13-15). In the landmark Study of Platelet Inhibition and Patient Outcomes (PLATO) trial, ticagrelor significantly reduced death from vascular causes, myocardial infarction, or stroke, without significantly increasing overall major bleeding in patients presenting with acute coronary syndromes (16).

Along with the advent of more potent antiplatelet pharmacotherapy, stent technology has also advanced in a concordant fashion with the introduction of safer and less thrombogenic

platforms. These devices, compared to their older-generation counterparts, yield significant reductions in thrombotic events that are durable over the long term (17). As a consequence, classical paradigms favoring a minimum of DAPT duration of 1 year, particularly in elective patients, are being challenged as PCI safety continues to evolve and improve. Randomized comparisons of different DAPT durations such as the OPTIMIZE and the PRODIGY trials suggest no increased risk for thrombotic events after only 3-6 months of DAPT in PCI patients treated primarily with novel generation devices (18-22).

1.1 Research hypothesis

The overall hypothesis of the current study is that three months post-PCI of dual antiplatelet therapy with aspirin and ticagrelor, continued monotherapy with ticagrelor alone versus ticagrelor plus aspirin for an additional year will be superior with respect to bleeding and non-inferior with respect to ischemic events in high-risk patients undergoing elective or urgent PCI.

This hypothesis will be tested in the following two specific aims:

Aim 1: To determine the impact of ticagrelor alone versus ticagrelor plus aspirin in reducing clinically relevant bleeding among high-risk patients who had PCI.
	
Hypothesis 1: A DAPT strategy of ticagrelor + ASA for 3 months followed by ticagrelor alone for an additional 12 months will be superior to ticagrelor plus aspirin with respect to clinically relevant bleeding (BARC \geq 2) in high-risk patients undergoing PCI.

Aim 2: To determine the impact of ticagrelor alone versus ticagrelor plus aspirin in reducing ischemic adverse events at one year among high-risk patients undergoing PCI
	
Hypothesis 2: A DAPT strategy of ticagrelor + ASA for 3 months followed by ticagrelor alone for an additional 12 months will be non-inferior to ticagrelor plus aspirin for with respect to ischemic adverse events at 1 year in high-risk patients undergoing PCI.

1.2 Rationale for conducting this study

Despite the trend and rationale for shorter DAPT durations following PCI, certain high-risk patients may derive additional benefit from potent and sustained platelet inhibition extending beyond 3 months after PCI. Defined by clinical and/or anatomic criteria, a short course of DAPT in such patients may provide sufficient protection against early stent-related thrombotic events while ongoing platelet inhibition may yield further reductions in systemic atherothrombosis. Among diabetics undergoing PCI, for example, Brar et al. previously demonstrated that the benefits of DAPT compared to antiplatelet monotherapy persisted irrespective of BMS or DES use, suggesting a systemic rather than stent-related effect (23). Analogously, results from the EXCELLENT trial suggested diabetics may derive additional benefit from prolonged DAPT (ASA + clopidogrel) compared to ASA alone (24). Findings from Dangas et al., which demonstrate a link between atherosclerosis and increased platelet

reactivity, provide a biological basis for potent platelet inhibition in high-risk patients characterized by diffuse vascular disease (25). These observations are clinically relevant as many patients undergoing elective or urgent PCI exhibit high-risk features, such as renal dysfunction, diabetes, peripheral arterial disease, that are associated with systemic atherosclerosis. Given the clear benefits of ticagrelor in the setting of high-risk ACS, it is plausible that ticagrelor alone will provide sufficient platelet inhibition to reduce thrombotic events compared to ticagrelor plus ASA among high-risk patients who have completed a requisite short course of DAPT.

Reduction in bleeding with ticagrelor alone while preserving of the anti-ischemic benefit associated with DAPT use would favor such a strategy in high-risk patients undergoing PCI.

Accordingly, the proposed study will examine the comparative safety and efficacy of a strategy of 3 month DAPT with ASA and ticagrelor followed by monotherapy using a potent agent (ticagrelor) compared to continued ASA and ticagrelor among high-risk patients undergoing PCI with DES. Our primary hypothesis is that, among such patients, use of ticagrelor alone will yield a significant reduction in clinically relevant bleeding while preserving anti-ischemic protection compared to the combination of ticagrelor and ASA.

1.3 Benefit/risk and ethical assessment

The potential benefits that subjects might realize by participating in this randomized trial is a reduction in clinically relevant bleeding for those who are randomly allocated to the placebo arm. Other benefits applicable to all subjects include close monitoring and surveillance for clinical events that will be performed by study personnel during the course of the trial.

The potential risks for subjects include an increased rate of thrombotic events for those who are randomized to the placebo arm and increased risk for bleeding in subjects randomized to the active treatment arm (low-dose ASA [81 mg – 100 mg]).

An independent data safety monitoring board will provide external oversight to ensure safety of all trial participants. In addition, subjects will be followed closely with periodic study contacts. Also, clinical equipoise exists for conducting a trial with this type of randomized comparison.

2. STUDY OBJECTIVES

2.1 Primary objective

The primary objective of this study is to determine the impact of antiplatelet monotherapy with ticagrelor alone versus DAPT with ticagrelor plus aspirin for 12 months in reducing clinically relevant bleeding among high-risk patients undergoing PCI who have completed a 3-month course of aspirin plus ticagrelor.

2.2 Secondary objective

The secondary objective of this study is to determine the impact of antiplatelet monotherapy with ticagrelor alone versus DAPT with ticagrelor plus aspirin for 12 months in reducing major ischemic adverse events among high-risk patients undergoing PCI who have completed a 3-month course of aspirin plus ticagrelor.

[figure not shown]
2.3 Exploratory objectives

Exploratory objectives include assessing the comparative safety and efficacy of the different DAPT regimens for individual components of the primary efficacy and secondary safety objectives.

3. STUDY PLAN AND PROCEDURES

3.1 Overall study design and flow chart

Figure 1 TWILIGHT Trial Design

3.2 Rationale for study design, doses and control groups

A randomized, double-blind study design was chosen as the most rigorous experimental approach to formally test the study hypotheses for the efficacy and safety of different DAPT regimens in high-risk patients undergoing PCI. Open label aspirin and ticagrelor per physician discretion will be given for the first 3 months after PCI. After 3 months, event-free subjects

will be randomized to placebo versus enteric-coated ASA for an additional 12 months. Open-label ticagrelor at a dose of 90 mg twice daily will be continued in all randomized subjects.

4. SUBJECT SELECTION CRITERIA

4.1 Inclusion criteria

High-risk patients who have undergone successful PCI with at least one locally approved drug eluting stent (DES) discharged on DAPT with aspirin and ticagrelor of at least 3 months intended duration will be eligible for the TWILIGHT study.

Enrollment into the study will require meeting at least one clinical inclusion AND at least one angiographic inclusion AND none of the exclusion criteria. A subject is considered enrolled if all these criteria are met and upon provision of informed consent.

Must meet AT LEAST ONE clinical inclusion criterion	Must meet AT LEAST ONE angiographic inclusion criterion
Adult patients ≥ 65 years of age Female gender Troponin positive acute coronary syndrome Established vascular disease defined as previous MI, documented PAD or CAD/PAD revascularization Diabetes mellitus treated with medications or insulin Chronic kidney disease defined as an estimated glomerular filtration rate (eGFR) <60 ml/min/1.73m ² or creatinine clearance (CrCl) <60 ml/min	Multivessel coronary artery disease (CAD)* (see Section 16) Target lesion requiring total stent length >30 mm Thrombotic target lesion(s) Bifurcation lesion(s) with Medina X,1,1 classification requiring at least 2 stents (see Section 16) Left main ($\geq 50\%$) or proximal LAD ($\geq 70\%$) lesion Calcified target lesion(s) requiring atherectomy
*The diagnosis of multivessel CAD may be established with the angiogram performed at enrollment or an earlier angiogram. A vessel previously treated with either a stent or bypass graft may also be considered diseased for purposes of meeting the multivessel CAD angiographic inclusion criterion.	

4.2 Exclusion criteria

Subjects should not enter the study if any of the following exclusion criteria are met:

- Under 18 years of age
- Contraindication to aspirin, as listed in Appendix D
- Contraindication to ticagrelor, as listed in Appendix E
- Planned surgery within 90 days
- Planned coronary revascularization (surgical or percutaneous) within 90 days
- Need for chronic oral anticoagulation
- Prior stroke
- Dialysis-dependent renal failure
- Active bleeding or extreme-risk for major bleeding (e.g. acute gastrointestinal ulcer or history of chronic gastrointestinal ulceration, gastrointestinal pathology with a raised risk for bleeding, malignancies with a raised risk for bleeding)
- Salvage PCI or STEMI presentation.
- Liver cirrhosis
- Life expectancy < 1 year
- Unable or unwilling to provide informed consent
- Women of child bearing potential as defined below:
A woman is considered of childbearing potential (WOBCP) following menarche and until becoming post-menopausal unless permanently sterile. Permanent sterilization methods include hysterectomy, bilateral salpingectomy and bilateral oophorectomy. A postmenopausal state is defined as no menses for 12 months without an alternative medical cause.
- Fibrinolytic therapy within 24 hours of index PCI
- Concomitant therapy with a strong cytochrome P-450 3A inhibitor or inducer
- Platelet count < 100,000 mm³
- Requiring ongoing treatment with aspirin ≥ 325 mg daily

5. STUDY CONDUCT

5.1 Restrictions during the study

Enrolled subjects should remain on study-provided open-label ticagrelor plus open-label aspirin for the first three months after index PCI followed by study-provided open-label ticagrelor plus blinded study drug for 12 months after randomization.

Unless clinically indicated, non-steroidal anti-inflammatory drugs (NSAIDs) and additional P2Y₁₂ inhibitors (ticlopidine, prasugrel, clopidogrel) should not be taken by study participants during the course of the trial. In addition, ticagrelor should be administered with caution in patients with history of hyperuricemia or gouty arthritis.

5.2 Subject randomization and initiation of investigational product

5.2.1 Procedures for randomization

The eligibility for randomization for all enrolled subjects will be evaluated at the in-person 3-month study visit. Subjects with any of the following will not be randomized:

- Refusal of randomization by subject or treating physician
- Withdrawal of consent
- Lost to follow-up
- Death
- Major bleeding (BARC Types 3b or greater)
- Occurrence of an ischemic event after PCI such as myocardial infarction, definite or probable stent thrombosis, ischemic stroke, coronary revascularization with drug-eluting stent
- No longer taking DAPT with aspirin and ticagrelor
- Non physician-guided cessation of aspirin or ticagrelor of 5 consecutive days or greater.
- Women of child bearing potential (as defined in Section 4.2)
- Renal failure requiring dialysis
- Current indication for oral anticoagulation or high dose aspirin

Randomization will be performed within the EDC system among subjects eligible for randomization. The EDC will allocate the treatment group assignment for the subject and provide study site research personnel the appropriate bottle ID number(s).

Upon randomization at the conclusion of the in-person 3-month visit, the study site research personnel will provide a 6-month supply of blinded investigational product (aspirin or matching placebo) and open-label ticagrelor.

Enrolled subjects who do not meet eligibility for randomization will have completed their protocol required activities and therefore will not receive any further study-provided medications. Their treating physician will also be notified that the patient's protocol-mandated study activities have concluded. Further antiplatelet therapy will be at the discretion of the subject's treating physician in accordance with local standard of care. Vital status of these subjects will be determined at the 18-month time point.

Enrolled subjects who do not meet eligibility for randomization *prior to* the in-person 3-month visit will not be required to complete the 3-month in-person visit.

5.3 Procedures for handling subjects incorrectly enrolled or randomized on investigational product

Subjects who are incorrectly enrolled will be immediately withdrawn from the study. The subject and the treating physician will be notified. If the subject has already been randomized, the investigational drug (aspirin or matching placebo) will be discontinued and further treatment will be as per standard of care. Subjects will be advised to continue therapy with ticagrelor until seen by their treating physician.

Subjects who are provided the incorrect investigational drug (study drug bottle(s) were not provided according to EDC randomization instructions) may be identified during monitoring procedure and/or drug reconciliation. In this case, the subject will be informed immediately and requested to return with all dispensed investigational drugs. The subject will then be provided with the correct investigational drug according to the randomization instructions. In addition, a protocol deviation form will be completed.

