5.8 Discontinuation of investigational product or study drug

Study-provided medications (open-label ticagrelor or blinded study drug) may require *temporary interruption* for the following reasons:

- 1. Surgery or invasive procedure:** Study-provided medications should be resumed after surgery once the risk of bleeding is no longer considered prohibitive in the judgment of the treating physician. Minor surgeries and procedures, including but not limited to tooth extraction, colonoscopy and endoscopy, may be safely performed on low-dose aspirin and therefore do not require temporary interruption of blinded study drug. However, if deemed necessary and at the discretion of the treating physician, open-label ASA may be substituted for blinded study drug in the peri-operative period. Blinded study drug may then be restarted at the discretion of the treating physician after completing the mandatory course of open-label ASA.
- 2. Balloon angioplasty or PCI with bare-metal stent:** In the event of coronary revascularization with balloon angioplasty alone or PCI with bare metal stent, blinded study drug may be temporarily interrupted for 2-4 weeks while patients receive open-label ASA at the discretion of the treating physician in accordance with local practice and standard of care. Blinded study drug may then be restarted at the discretion of the treating physician after completing the mandatory course of open-label ASA.
- 3. Clinically Significant Bleeding:** Study-provided medications should be temporarily interrupted pending resolution of the acute bleeding episode and

may be restarted at the discretion of the treating physician if deemed clinically safe and in accordance with local practice and standard of care.

4. Details surrounding the date, duration and reason for each episode of temporary interruption should be entered in the appropriate section of the EDC.

Study-provided medications (open-label ticagrelor or blinded study drug) may require *permanent discontinuation* for the following reasons:

1. Patient decision: The patient is at any time free to discontinue treatment, without prejudice to further treatment.
2. Investigator's decision:
 - a. Incorrectly enrolled patient in whom the inclusion/exclusion criteria violation would put the patient at undue risk

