 - b. Adverse Events felt to be related to either study medication for which Investigator feels continued treatment would put the patient at undue risk, such as severe or life-threatening bleeding, myocardial infarction, stent thrombosis, ischemic stroke or coronary revascularization with a DES.
3. Renal failure requiring dialysis
4. Chronic oral anticoagulation
5. Details surrounding the date, duration and reason for permanent discontinuation of study medication should be entered in the appropriate section of the EDC.
6. In the event of permanent discontinuation of either study medication, further antiplatelet therapy is at the discretion of and is to be provided by the patient's treating physician. Any remaining study-provided medication should be returned to the local site at the next scheduled follow-up visit. Although these patients will no longer receive study-related medication, follow-up will continue in all randomized patients until end of study

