5.9 Withdrawal from study

Each enrolled subject shall remain in the trial until completion of the required follow-up period. However, a subject's participation in any clinical trial is voluntary and the subject has the right to withdraw at any time without penalty or loss of benefit. Conceivable reasons for discontinuation may include, but not be limited to, the following:

- Subject voluntary withdrawal
- Subject withdrawal by physician as clinically indicated
- Subject lost-to follow-up

The reason for subject discontinuation must be documented in the eCRF and source documents. The individual site Principal Investigators must also report all subject discontinuations to their IRB/EC as defined by their institution's procedure.

All data from evaluations and treatments performed prior to the withdrawal should be documented in the eCRFs. Source documents that pre-date the withdrawal should be submitted as required by the protocol. No data that post-dates the withdrawal will be collected.

Once a subject has withdrawn from the trial, no further follow-up contact will be performed. However, vital status may be obtained from public records. Medical therapy after stopping the study will be as prescribed by the subject's physician.

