12.1 Description of analysis sets

The Enrolled Population consists of all subjects who signed informed consent.

The intention-to-treat (ITT) population will consist of all subjects who have been randomized (i.e. when the subject number and allocated treatment are recorded in the EDC). Subjects will be analyzed in the treatment group assigned by the EDC.

The per-protocol population (PP) will consist of all randomized subjects without any major deviations from the protocol. The following deviations will lead to exclusion from the PP population

- Subjects not receiving the assigned treatment as allocated by the EDC or no treatment at all
- Non-compliance to study drug (aspirin or placebo) or ticagrelor. Non-compliance is defined as taking less than 80% of dispensed tablets based on manual pill bottle count at each study visit.

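### Section 5.3 withdraws incorrectly enrolled subjects from the study even after randomization, which ends outcome collection under 5.9, while 5.8 keeps all randomized patients in follow-up

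*Combined protocol and SAP*

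**What the plan says.** Section 5.3 gives the rule for eligibility errors: "Subjects who are incorrectly enrolled will be immediately withdrawn from the study". The same paragraph then turns to randomized subjects: "If the subject has already been randomized, the investigational drug (aspirin or matching placebo) will be discontinued", with later treatment left to standard of care. It does not say that their follow-up continues.

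Section 5.9 sets out what withdrawal from the study means. No further contact is made, and "No data that post-dates the withdrawal will be collected". The one exception is optional: "However, vital status may be obtained from public records". Its open-ended list of reasons includes "Subject withdrawal by physician as clinically indicated".

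Section 5.8 lists, among the reasons for permanently stopping study medication, "Incorrectly enrolled patient in whom the inclusion/exclusion criteria violation would put the patient at undue risk". Its closing item, on patients who have permanently stopped, says that "follow-up will continue in all randomized patients until end of study".

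Section 12.1 says: "The intention-to-treat (ITT) population will consist of all subjects who have been randomized". It makes no exclusion for eligibility violations. ITT is the primary set for the bleeding endpoint (12.1.1, 12.2) and the secondary set for the ischemic endpoint (12.1.2). The censoring rule in 12.2 ties the last contact date to withdrawal of consent and loss to follow-up only.

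**The concern.** Stopping a drug and stopping follow-up are separate decisions. Section 5.8 keeps them apart; section 5.3, read with 5.9, merges them. A randomized subject found to be ineligible stays in the ITT denominator, but under 5.3 stops contributing bleeding, infarction and stroke outcomes, although the subject has neither withdrawn consent nor been lost.

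That is avoidable missing data in the primary bleeding analysis. It may also be informative, since subjects who breach an entry criterion may differ in risk from those who do not. In addition, with about 100 sites planned, some may act on 5.3 and others on 5.8, so identical cases could be handled differently.

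**Working it through.** **Comparing the sections.** Take a randomized subject later found not to have met the entry criteria.

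| Question | 5.3 with 5.9 | 5.8 |
|---|---|---|
| Who is covered? | All incorrectly enrolled subjects | Those whose violation poses undue risk |
| In the study? | Withdrawn at once | Remains |
| Contacts? | None | Continue to end of study |
| Bleeding, MI, stroke? | Not collected after withdrawal | Collected |
| Death? | Optional, public records | Collected |
| In ITT (12.1)? | Yes | Yes |

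For an undue-risk violation both columns apply and contradict each other. For any other violation only 5.3 speaks directly, and it ends follow-up.

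**Size: inputs.** From 12.3: 8200 randomized (4100 per arm), control bleeding rate 4.5%, relative reduction 28%, loss 2%, non-compliance/cross-over 4%, two-sided 0.05, 80% power. The share *f* of randomized subjects withdrawn under 5.3 is not in the documents. I assume 0.5% to 3%, with all withdrawn soon after randomization, which is the worst case for any given share.

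**Reproducing the plan.**
- Experimental rate without dilution: 0.045 × 0.72 = 0.0324.
- With 4% cross-over diluting the experimental arm: p2 = 0.045 × (1 − 0.28 × 0.96) = 0.0329.
- The two-proportion formula then needs 8032 subjects in total; 8032 / 0.98 = 8196, against the stated 8200.
- Power = Φ{[(p1 − p2)√n − 1.96√(2p̄(1 − p̄))] / √(p1(1 − p1) + p2(1 − p2))}, where p̄ is the mean of p1 and p2. With n = 4100 × 0.98 = 4018 per arm, power is 80.0%.

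**Adding the withdrawals.** Replace n by 4018 × (1 − f). Expected first bleeds use the mean of 4.5% and 3.24%, which is 3.87%; in total 8200 × 0.0387 = 317.

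| f (assumed) | Subjects, 8200 × f | First bleeds not collected, × 0.0387 | Bleeding power |
|---|---|---|---|
| 0 | 0 | 0 | 80.0% |
| 0.5% | 41 | 1.6 | 79.8% |
| 1% | 82 | 3.2 | 79.6% |
| 2% | 164 | 6.3 | 79.2% |
| 3% | 246 | 9.5 | 78.8% |

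The largest loss in this range is 80.0 − 78.8 = 1.2 percentage points. I make no calculation against the 1.6-point ischemic margin: that primary test is in the per-protocol set, and deaths may still be found in public records.

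**The case against.** The strongest reply is that this is loose drafting. Enrollment takes place at PCI, three months before randomization, so withdrawal may be meant for subjects not yet randomized. The sentence addressed to randomized subjects speaks only of stopping the drug, and 5.8 then supplies their follow-up rule. Section 5.9 opens by expecting subjects to stay until follow-up is complete, and its reasons do not name incorrect enrollment. This reading is possible, but the first sentence of 5.3 has no such limit, the list in 5.9 is open, and for violations without undue risk 5.8 does not name the case. A site that follows the text literally would stop collecting data.

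Other points limit the size, and they stand:
- Eligibility is checked again at the 3-month visit (5.2.1 and the schedule of data collection), so errors found by then never reach the ITT set.
- Subjects, sites, treating physicians and academic research center staff are blinded, so there is no stated route by which discovery of an error would depend on arm.
- Data from before withdrawal are kept. If a bleed prompts the record review that uncovers the error, that first bleed still counts.
- Some of these withdrawals could fall within the 2% loss already planned, which would make the added power loss smaller than in the table.

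The censoring point is also minor. The last contact date is the natural extension to a subject withdrawn under 5.3; the text simply does not say so.

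**Conclusion.** The concern holds. For a randomized, incorrectly enrolled subject, 5.3 with 5.9 and 5.8 give opposite follow-up instructions, and following 5.3 discards obtainable outcomes from a subject who remains in the primary bleeding analysis set.

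The numerical effect is small: at most about 1.2 points of power and about 10 of 317 first bleeds, on an assumed share of up to 3% with all withdrawals soon after randomization. No differential loss between arms has been shown, and the documents do not allow the direction of any bias to be stated. The case rests on the contradiction and on avoidable missing ITT outcomes, not on power. It should be corrected. Confidence is high on the reading of the text; the size rests on the assumed share.

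**What to change.** 1. **Section 5.3.** Separate leaving the study from stopping study drug. Suggested text: *Randomized subjects found to have been incorrectly enrolled remain in scheduled follow-up to 18 months and in the ITT population, unless they withdraw consent, have no valid consent, or are lost to follow-up.* This is the essential change.
2. **Section 5.9.** State that a physician's decision does not by itself end outcome collection in a randomized subject who still consents. This goes beyond the conflict between 5.3 and 5.8, but without it the same gap stays open by another route.
3. **Section 12.2.** Name the censoring date for any randomized subject who is nevertheless withdrawn, and report the number, arm and reason. This is a detail for completeness.

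Sections 5.3 and 5.8 also differ on when study drug stops after incorrect enrollment. The sponsor must reconcile those passages; no drug rule is proposed here.

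The cost is about three sentences of protocol wording. The 4-, 9-, 15- and 18-month contacts for randomized subjects already exist.
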